**Exclusion criteria**

- Immature teeth with open apices
- Different surgical technique

**5.3 Methods**

- *Evaluation of medical history*
- *Interpretation of existing x-rays*

**Any known or foreseeable factors that may affect the results of the study or its interpretation:**

- Missing data

## 6. Statistical considerations

Andreasen et al. determined in their long-term study over 370 transplanted premolars that with completed root growth (and consequently closed foramen apical) only in 60% of cases does periodontal healing occur, while this is to be expected in immature teeth in 90% of cases.

If one compares the pulpal healing in teeth with completed and non-completed root growth, one even comes to a difference of 15 to 96%.

Since this is a retrospective data analysis, the statistical evaluation is carried out by means of descriptive statistics. The result is then compared with published success rates in the subject-specific literature. (Chi square test) It should be shown that the success rate of transplantation of teeth with completed root growth according to the presented method

does not differ from the success rate of transplanted immature teeth with open foramen apical.

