## Synopsis

Sponsor	Univ. [name]. [name] Department of Dental Medicine and Oral Health, Division of Oral Medicine and Orthodontics Medical University of Graz
Title	Revascularization of autotransplanted adult teeth – retrospective analysis of a novel technique
Population	Patients who experienced autotransplantation of adult teeth
Study design	Retrospective data analysis
Objectives	Evaluation of the success rate of reperfusion of autotransplanted adult teeth
Outcome variables	Primary outcome variable: Reperfusion of the transplanted tooth Secondary outcome variable: Periodontal healing
Participants	17 -20 patients
Timetable	Retrospective analysis and data evaluation over 1 month
Inclusion criteria	
 
• Patients who experienced one or multiple autotransplantations of teeth
 
• At least one year of follow-up
 

Exclusion criteria	
 
• Immature teeth with open apices
 
• Different surgical technique
 

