## 2. Methods:

By a retrospective study design, clinical and radiological data regarding patients who experienced tooth transplantation with concomitant root tip resection between July 2017 and June 2020 will be obtained and analyzed. Clinical and radiological findings will be evaluated regarding periodontal and pulpal healing.

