**c) Outcome Variables:**

**Primary Outcome:** Reperfusion of transplanted teeth

**Secondary Outcome:** Periodontal Healing, Tooth loss

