**5.2 Participants****Inclusion criteria**

- Patients who experienced one or multiple autotransplantations of teeth
- At least one year of follow-up

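### Periodontal healing: a proportion over unequal follow-up of one year or more is to be tested against published rates, and the only ones quoted come from a long-term study

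*Protocol*

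**What the plan says.** Section 2 of the Protocol takes transplantations performed "between July 2017 and June 2020". The inclusion criteria in section 5.2 require "At least one year of follow-up" and set no maximum. Section 4 c lists "Reperfusion of transplanted teeth" as the primary outcome and "Periodontal Healing, Tooth loss" as secondary outcomes, none with an assessment time. The Synopsis gives the size as "17 -20 patients".

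Section 6 provides for descriptive statistics, followed by a chi-square comparison with success rates from the literature. The stated aim is to show that mature teeth treated with the new method do no worse or better than transplanted immature teeth. Two pairs of rates are given:

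- **Periodontal healing**, attributed to a "long-term study over 370 transplanted premolars": "only in 60% of cases does periodontal healing occur, while this is to be expected in immature teeth in 90% of cases".
- **Pulpal healing**: "one even comes to a difference of 15 to 96" percent, with neither a source nor a length of follow-up attached to the sentence.

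**The concern.** Three years of transplant dates and a one-year minimum give teeth that have been watched for different lengths of time. A chi-square on a simple proportion counts a tooth seen for one year the same as a tooth seen for several. The periodontal rates on the other side of the comparison come from a study that the Protocol itself labels long-term.

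If periodontal failures emerge gradually, a status at one to a few years and a long-term status are different quantities, and the younger cohort looks better for that reason alone. Because the aim is to find no difference from the higher (immature) rate, the error runs towards the desired conclusion. A method that does nothing for periodontal healing could then be reported as matching immature teeth. Among foreseeable influences on interpretation, section 5.3 mentions only missing data.

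**Working it through.** The Protocol gives no power, margin or significance level, so there is no figure of its own to reproduce. The check asks how often a no-benefit technique would yield a non-significant result against the immature rate.

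**Inputs from the Protocol.** 17 to 20 patients (Synopsis); periodontal healing 60% mature and 90% immature, pulpal healing 15% and 96% (section 6); follow-up of at least one year (section 5.2).

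**Assumptions.** One tooth per patient; two-sided level 0.05; one-sample chi-square with the published rate taken as fixed; long-term periodontal healing of 60% under no benefit.

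**Step 1: which results are non-significant against 90%.** The statistic is (x − 0.9n)² / (n × 0.9 × 0.1), compared with 3.84.

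- n = 20: x = 16 gives (16 − 18)²/1.8 = 2.22, non-significant; x = 15 gives 9/1.8 = 5.00, significant. So 16 or more healed counts as no difference.
- n = 17: x = 13 gives (13 − 15.3)²/1.53 = 3.46, non-significant; x = 12 gives 10.89/1.53 = 7.12, significant. So 13 or more.

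**Step 2: chance of that result, by exact binomial probability.**

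| True crude healing rate | n = 20 | n = 17 |
|---|---|---|
| 60% (follow-up matched) | 5% | 13% |
| 68% | 18% | 32% |
| 75% | 41% | 57% |
| 80% | 63% | 76% |
| 85% | 83% | 90% |

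The 68% and 80% rows correspond to early failure. If a share s of the 40% failures falls within year 1, one-year healing is 1 − 0.4s, which gives 68% at s = 0.8 and 80% at s = 0.5.

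**Step 3: what gradual failure would do.** With a constant hazard reaching 60% healed at T years, healing at t years is 0.6^(t/T). Take follow-up as uniform over 1 to 4 years, which corresponds to an assumed data cut in mid-2021. The mean crude rate is then (e^(−h) − e^(−4h)) / (3h), with h = −ln(0.6)/T.

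- T = 5: h = 0.1022; (0.9029 − 0.6645)/0.3065 = 0.778; chance of non-significance at n = 20 is 53%.
- T = 10: h = 0.0511; (0.9502 − 0.8152)/0.1532 = 0.881; chance is 92%.

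**Step 4: the same check for reperfusion.** Against 96%, non-significance needs at least 18 of 20: x = 18 gives (18 − 19.2)²/0.768 = 1.88, and x = 17 gives 4.84/0.768 = 6.30. At the quoted mature rate of 15% the chance is effectively zero. Even if short follow-up lifted the crude rate to 50%, it would be 0.02% (0.12% at n = 17, where 15 are needed).

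**The case against.** A reader might infer that the whole study is exposed and that a useless technique could pass on its primary outcome. The Protocol does not support that. The long-term label is attached only to the 60% and 90% periodontal figures. The pulpal rates carry no horizon, and step 4 shows that the gap between them is too wide for a modest lift to bridge. The Introduction also describes pulp necrosis as a direct result of the lost blood supply, so nothing in the text suggests that pulp failures stay hidden for years. Nor can the argument be carried over to tooth loss as a biased comparison, because no tooth-loss rate is quoted to compare with.

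Other objections deserve weight:

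- **Choice of comparator.** Section 6 refers to the literature in general and does not expressly name 60% and 90% as the test values, so a comparator with a matching horizon could still be chosen. That is so, but they are the only periodontal rates given, and nothing in the section requires horizons to match.
- **Direction.** The Protocol does not say that periodontal failure accumulates. If healing is slow to show, short follow-up would work against the technique. This makes the direction conditional; it does not make the two quantities comparable.
- **Size.** Assuming that almost every tooth is seen for only one year would give still higher chances, about 96% at a crude 90.3%. The unequal follow-up in the plan argues against that reading, so it should not serve as a headline.
- **Other causes.** The small sample and the treatment of non-significance as equivalence, without a margin, create risk of their own. Even with matched follow-up it is 5% to 13%. That part does not belong to this point.
- **SAP content.** Time points are often left to an analysis plan. Here, however, the Protocol itself fixes the test and the conclusion to be drawn.

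**Conclusion.** The point stands for periodontal healing, a secondary outcome. As written, section 6 can set a proportion from unequal follow-up, with no common assessment time, against rates from a study described as long-term. If periodontal failures appear over time, this favours the conclusion of no difference from immature teeth.

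At n = 20, the chance of wrongly reaching that conclusion rises from 5% with matched follow-up to 18% if most failures come early, and to 53% to 92% under gradual failure. The sample size is the same throughout, so under these assumptions the rise is due to follow-up alone. The benchmark's horizon, the failure pattern and the data cut are not in the Protocol, so the size is uncertain across that whole range. The change is advisable rather than essential, since the primary outcome is not shown to be affected.

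**What to change.** In section 6:

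1. Define periodontal status in a stated time window, for example at the visit nearest 12 months where records allow.
2. Compare it only with a published rate at a similar horizon. Where none exists, report the proportion with an exact confidence interval and the distribution of follow-up, without a test against the long-term figure.
3. Report tooth loss by Kaplan-Meier from the date of transplantation, censoring at the last visit.

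This changes wording only, provided that transplant and visit dates are in the records. The price is that some comparisons with 60% and 90% become descriptive. Teeth without a visit in the window count as missing; since the study relies on existing x-rays, a film near 12 months is not assured for every tooth.

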**b) Hypothesis**

Simultaneous resection of the root tip leads to a higher rate of reperfusion.

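### Section 6 wants to show no difference from immature teeth, but its chi-square test of no difference cannot show that with 17 to 20 patients, and section 4b states another hypothesis

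*Protocol*

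**What the plan says.** Section 6 (Statistical considerations) calls the evaluation descriptive and then adds a test: "The result is then compared with published success rates in the subject-specific literature. (Chi square test"). It goes on to say what this should demonstrate, namely that success with the technique in teeth with completed root growth "does not differ from the success rate of transplanted immature teeth with open foramen apical".

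The same section gives two pairs of published rates:
- **Periodontal healing:** in teeth with completed root growth "only in 60% of cases does periodontal healing occur, while this is to be expected in immature teeth in 90% of cases".
- **Pulpal healing:** comparing completed with non-completed root growth, "one even comes to a difference of 15 to 96" percent.

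The primary outcome in section 4c is "Reperfusion of transplanted teeth". The hypothesis in section 4b is directional and names no comparator: "Simultaneous resection of the root tip leads to a higher rate of reperfusion". The Synopsis plans "17 -20 patients" without a derivation. Section 5.2 admits "Patients who experienced one or multiple autotransplantations of teeth", so there may be more teeth than patients; the number of teeth is not given.

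**The concern.** The null hypothesis of the chi-square test is that the rates are equal. A significant result contradicts the section 6 aim, but a non-significant one does not establish it, because it may only mean that there were too few teeth. To show similarity, the plan has to say how large a shortfall would still count as similar and then exclude anything larger. The protocol gives no such limit.

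If the stated aim is judged by the stated test, a technique moderately worse than transplantation of immature teeth could be reported as no different from it.

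The aim and the hypothesis are also different claims. Section 6 looks for similarity to immature teeth. Section 4b expects higher reperfusion, and the Introduction, which describes reduced revascularization in mature teeth, suggests that this means higher than in mature teeth without resection. The two claims need different reference rates (96% and 15% for pulpal healing), and section 6 states an aim only for the first.

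**Working it through.** The protocol has no sample size calculation to reproduce, so the check is what the named test can and cannot distinguish.

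**Inputs from the protocol.** n = 17 to 20 (Synopsis); published rates of 96% and 15% (pulpal) and 90% and 60% (periodontal) from section 6.

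**Assumptions.** Two-sided 5%; published rate treated as a fixed number; one tooth per patient; published pulpal healing taken as the counterpart of reperfusion. The true rates below are illustrative. Paired figures are n=17 / n=20.

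**1. Results that count as not different.** With x successes and reference rate p0, the statistic is (x − n·p0)² / (n·p0·(1 − p0)), compared with 3.84.
- Against 96%, n=17: x=15 gives (15 − 16.32)²/0.6528 = 2.67 (p=0.10), and x=14 gives 8.25. Non-significant from 15/17 upward.
- Against 96%, n=20: x=18 gives (18 − 19.2)²/0.768 = 1.88 (p=0.17), and x=17 gives 6.30. Non-significant from 18/20 upward.
- Against 90%: non-significant from 13/17 or 16/20 upward.

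The exact 95% intervals are 64–99% for 15/17 and 68–99% for 18/20. An exact binomial test gives the same cut-offs against 96% and 90%. The chi-square approximation is itself poor here, since only 17 × 0.04 = 0.68 or 20 × 0.04 = 0.8 failures are expected at 96%.

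**2. Probability of a non-significant result when the technique is worse.** This is the binomial probability of the counts in step 1. For a true 85% and n=17, P(15) + P(16) + P(17) = 0.267 + 0.189 + 0.063 = 0.520.

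| True rate | Published rate | n=17 | n=20 |
|---|---|---|---|
| 85% | 96% | 52% | 41% |
| 80% | 96% | 31% | 21% |
| 70% | 96% | 8% | 4% |
| 15% | 96% | about 0 | about 0 |
| 75% | 90% | 57% | 42% |
| 60% | 90% | 13% | 5% |

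**3. One result, two opposite readings.** For periodontal healing, the counts that are non-significant against 60% are 7–14 of 17 and 8–16 of 20. Those that are non-significant against 90% start at 13 and 16. So 13/17, 14/17 and 16/20 fit both the mature and the immature rate. At 18 and 19 teeth the overlap is a single count (14 and 15). At a true 75% such a result occurs with probability 41% / 19%. The exact 95% intervals are 50–93% for 13/17 and 56–94% for 16/20.

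**4. Best possible case.** With no failures the exact lower limit is 0.025^(1/n), which is 80.5% for 17/17 and 83.2% for 20/20. The smallest shortfall that could be excluded is 96 − 80.5 = 15.5 or 96 − 83.2 = 12.8 points for pulpal healing, and 90 − 80.5 = 9.5 or 90 − 83.2 = 6.8 points for periodontal healing.

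**5. More teeth than patients.** With an assumed 25, 30 or 40 independent teeth, non-significance is still 25%, 32% and 26% for a true 85% against 96%, and 38%, 35% and 18% for a true 75% against 90%. With fixed reference rates the overlap in step 3 disappears at these numbers.

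**6. Published rate as a second sample.** In a 2×2 table with an assumed 50, 100, 200 or 300 published immature teeth at 96%, the lowest non-significant count out of 17 is 14, 15, 15, 15 without continuity correction and 13, 14, 14, 15 with it. The cut-offs are the same as in step 1 or more lenient.

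**7. The section 4b claim.** The exact 95% lower limit exceeds 15% from 7/17 (18.4%) or 7/20 (15.4%) upward. If the true rate were 50%, that would be reached with probability 83% / 94%.

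**The case against.** The strongest reply is that this is a small descriptive record review. Section 6 says so before it mentions any test, and reporting rates beside published ones is largely planned already. That is true, but the section then adds a test and a statement of what should be shown, and those two do not fit together. A later analysis plan could add a margin, but the protocol's own pairing of aim and test would still be wrong as it stands.

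Several narrower points stand and limit the finding:
- Large shortfalls would usually be detected (table in step 2), so the risk is confined to moderate ones.
- The double reading in step 3 concerns a secondary outcome and few counts, and depends on about one tooth per patient. Its disappearance at 25 or more teeth holds for fixed reference rates only.
- Section 6 refers to published rates in the plural and quotes the 15%, so a comparison with it is not ruled out. What is missing is the link to section 4b.
- Higher than mature teeth and no different from immature teeth can both be true. They are different claims rather than contradictory ones. That section 4b means mature teeth is an inference from the Introduction.
- Section 6 does not say whether its success rate is pulpal or periodontal, so both were checked.

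**Conclusion.** The concern holds. A chi-square test without a margin cannot establish the section 6 aim at any sample size. With 17 to 20 teeth, non-significance is close to an even chance for shortfalls of 11 points from 96% or 15 points from 90%, and even a series without failures leaves a deficit of roughly 13 to 16 points from 96% open. These figures rest on one tooth per patient, a fixed published rate and two-sided 5%. The logical point needs none of those assumptions.

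Separately, section 4b and section 6 state different claims, and section 6 does not tie the section 4b claim to a reference rate, although this cohort could address it against 15%. The point should be corrected before the records are analysed. It does not call the data collection into question.

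**What to change.** In section 6:
1. Remove the aim of showing no difference from immature teeth.
2. Report reperfusion and periodontal healing per tooth with exact (Clopper-Pearson) 95% confidence intervals, or intervals that allow for several teeth per patient, beside all four published rates: 15% and 96% pulpal, 60% and 90% periodontal.
3. State that p>0.05 will not be read as support for no difference.
4. Name the comparator for section 4b. If the published rate for completed root growth is meant, say that it is the 15% for pulpal healing.
5. If a similarity claim is kept, allow it only when the lower confidence limit exceeds the published immature rate minus a justified margin, fixed before the records are analysed. Add that 17 to 20 independent teeth can exclude, at best, deficits of about 13 to 16 points from 96% and 7 to 10 points from 90%.

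The cost is a rewording of section 6 and its link to section 4b, with no new patients or data. The price is a more modest conclusion about immature teeth.

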## 7. Data management

Data will be anonymized and recorded in an excel document.

The statistical analysis of the data is carried out by DI [name].

The collection, transfer, storage and evaluation of personal data within this study is carried out in accordance with legal provisions (Datenschutz-Grundverordnung, DSGVO).

## 8. Legal basis

### 8.1 General

Guidelines of the Declaration of Helsinki apply.

### 8.2. Vote of the Ethics Committee

Since this is sensitive patient data, it can only be started if the approval opinion of the responsible ethics committee is available.

